### **1.0 Objectives**

*1.1 Describe the purpose, specific aims, or objectives of this research. Specifically, explain why it is important to do the study.*

Historically, pregnant women were advised to refrain from exercise due to concerns of maternal and fetal risk such as preterm delivery, low infant birth rate and fetal stress. Despite current research that has demonstrated substantial benefits for maternal, fetal, and infant health, only 9-15% of pregnant women meet the current physical activity recommendations. In addition, pregnancy exercise research is confounded by a lack of randomized controlled trials (RCT) that include diversity in participant demographics, specifically inner city populations, and difficulty accurately quantifying weekly exercise volume. We propose a pilot RCT investigating two different approaches to exercise intervention across a spectrum of demographics that we believe will result in improved exercise adherence as well as in maternal and infant health outcomes.

*1.2 State the hypothesis to be tested, if applicable.*

*NOTE: A hypothesis is a specific, testable prediction about what you expect to happen in your study that corresponds with your above listed objectives.*

Specific Aim #1: To determine the feasibility of two types of exercise interventions (supervised & home exercise) in terms of design, implementation and adherence. Our working hypothesis is that both supervised and home exercise interventions will be implementable as designed in pregnant women as evidenced by recruitment, eligibility, retention, follow-up and exercise adherence from 1st trimester through 6-months post-natal at a 60% rate, but that adherence to the two types of exercise interventions will differ by demographic. A secondary exploratory hypothesis is that we will be able to successfully recruit and retain 50% of our pregnant women from the Syracuse Community Health Center (primarily women with lower resources).

Specific Aim #2: To determine the appropriateness of the outcome measures proposed for the exercise intervention in detecting changes in maternal aerobic fitness, quality of life (QOL), fatigue, sleep quality, depression, and weight change throughout pregnancy and 6-months post-natal as measured by the Balke Ware submaximal test; SF-12 Generic Quality of Life (QOL); Multidimensional Fatigue Inventory (MFI); Pittsburgh Sleep Quality Index (PSQLI); Center for Epidemiologic Studies Depression Scale (CES-D); Edinburgh Postnatal Depression Scale (EPDS); and the Pregnancy Physical Activity Questionnaire (PPAQ). Our working hypothesis is that the above outcome measures will be able to detect changes in maternal outcome measures in both exercise groups.

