## 2.0 Scientific/Safety Endpoints

*2.1 Describe the scientific endpoint(s), the main result or occurrence under study.*

*NOTE: Scientific endpoints are outcomes defined before the study begins to determine whether the objectives of the study have been met and to draw conclusions from the data. Include primary and secondary endpoints. Some example endpoints are: reduction of symptoms, improvement in quality of life, or survival. Your response should not be a date.*

The scientific endpoint of this project is determining if the study is feasible in terms of the proposed approach and if the planned outcome measures are appropriate for detecting change in the maternal dependent variables in all three participant groups.

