## **5.0 Data Management and Analysis**

*5.1 Describe the data analysis plan, including any statistical procedures. This section applies to both quantitative and qualitative analysis.*

Statistical analysis used to determine feasibility of the exercise intervention will include general descriptive statistics to assess recruitment, eligibility, retention, follow-up and exercise adherence. In addition, we will conduct a survey and interview of subjects related to acceptability to participate in EX and HOMEEX and discuss barriers to regular exercise which will be analyzed using descriptive statistics and a phenomenological approach. To determine the feasibility of maternal and infant outcomes, Kruskal-Wallis and Friedman's ANOVA will be used to investigate between group and within group differences. Relationships between variables will be analyzed using Spearman correlation coefficient. Because this is a feasibility study, the results will be used as preliminary data to apply for future funding and also will provide variable quantitative and qualitative data for validating interventions that can increase adherence to exercise guidelines during pregnancy in women with different ethnic and socioeconomic backgrounds.

*5.2 If applicable, provide a power analysis for the number of subjects to be included. If qualitative research, so state, and provide general justification for the total number of subjects proposed.*

*NOTE: This may not apply to certain types of studies, including chart/records reviews, survey studies, or observational studies. This question is asked to elicit whether the investigator has an adequate sample size to achieve the study objectives and justify a conclusion.*

This is a pilot project aimed to investigate feasibility of approach and appropriateness of maternal outcome measures. If the working hypotheses are supported, the next phase will be a large, randomized intervention study. Pilot data from this project can be utilized in the power analysis for the larger study.

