## **6.0 Local Number of Subjects**

6.1 *Indicate the total number of subjects who will be enrolled or records that will be reviewed through Upstate.*

No more than 18 total participants (six per group)

6.2 *If applicable, indicate your screen failure rate, i.e., how many subjects you expect to screen to reach your target sample.*

54 (anticipate that for every three women screened, one will participate in the study)

6.3 *Justify the feasibility of recruiting the proposed number of eligible subjects within the anticipated recruitment period. For example, how many potential subjects do you have access to? What percentage of those potential subjects do you need to recruit?*

The feasibility of recruitment is part of what is being investigated in this pilot project and findings from this project will inform the recruitment plan of the future large intervention study. The plan for the pilot is to recruit no more than 18 (six per group) low risk pregnant women with a singleton pregnancy from Syracuse Community Health Center (50%), University OB/GYN Associates, and Upstate Community OB/GYN. All women will be enrolled during the 1st trimester (6 to 13-weeks' gestation) and without absolute contraindications to moderate intensity exercise during pregnancy as defined by American College of Sports Medicine (ACSM) and American College of Obstetricians and Gynecologists (ACOG). All participants will be cleared for exercise by their OB/GYN.

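### Does the plan's own screening forecast (18 of 54, 33%) already miss the 60% feasibility rate in Aim 1?

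*Combined protocol and SAP*

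**What the plan says.** Section 1.2 (Specific Aim #1) states the working hypothesis that both exercise programmes can be delivered as designed, "as evidenced by recruitment, eligibility, retention, follow-up and exercise adherence from 1st trimester through 6-months post-natal at a 60% rate". A secondary, exploratory hypothesis is that the team can "recruit and retain 50% of our pregnant women from the Syracuse Community Health Center".

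Section 2.1 makes feasibility the endpoint: "The scientific endpoint of this project is determining if the study is feasible in terms of the proposed approach". Section 5.1, repeated in section 11.0, says the analysis will use "general descriptive statistics to assess recruitment, eligibility, retention, follow-up and exercise adherence". Section 5.2 links the result to what follows: "If the working hypotheses are supported, the next phase will be a large, randomized intervention study".

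The numbers are in section 6.0. Section 6.1 sets the size: "No more than 18 total participants (six per group"). Section 6.2, answering a prompt about screen failures, gives "54 (anticipate that for every three women screened, one will participate in the study"). Section 6.3 adds that "The feasibility of recruitment is part of what is being investigated in this pilot project". The timetable in section 11.1 counts recruitment as six women in each of the three groups, and section 12.1 allows three months for enrolment.

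**The concern.** Recruitment and eligibility appear in the same list as retention, follow-up and adherence, and the 60% rate follows the whole list. The only place where the plan gives both a number screened and a number enrolled is section 6.0, and that ratio is one in three. Read together, the plan seems to set a feasibility bar that its own forecast fails.

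The 60% rate is the main numeric threshold for the study's endpoint, and section 5.2 makes the larger trial depend on the hypotheses being supported. If the denominator is chosen only after the data are in, the same enrolment could be called a success or a failure. With 54 screened, 60% means 33 women on one reading and 11 on another, and every enrolment from 11 to 18 would pass one and fail the other.

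**Working it through.** **Inputs.** Threshold 60% (section 1.2); cap of 18 enrolled, six per group (6.1); 54 screened, one participant per three (6.2).

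**The plan's own figure.** 18 × 3 = 54, so section 6.2 is internally consistent. The implied yield is 18/54 = 33.3%, which is 60 − 33.3 = 26.7 percentage points below 60%.

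**The forecast under each reading of the 60% rate**

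1. *Enrolled / screened.* For 18 enrolled, at most 18/0.60 = 30 could be screened. With 54 screened, 0.60 × 54 = 32.4, so 33 must enrol, above the cap of 18. If the true yield is one in three, the binomial chance of 33 or more from 54, ignoring the cap, is about 0.00003. This reading conflicts with the forecast.
2. *Enrolled / target of 18.* 18/18 = 100%. The bar is 0.60 × 18 = 10.8, so 11 women (11/18 = 61.1%). No conflict.
3. *One screening step alone.* Eligible/screened can reach 60% (33/54 = 61.1%), and so can enrolled/eligible (18/30 = 60.0%). No conflict.
4. *Both steps at 60%.* The required yield is 0.60 × 0.60 = 36%, which is 18/0.36 = 50 screened for 18 enrolled. The forecast of 33.3% falls narrowly short: with 33 eligible, enrolled/eligible is 18/33 = 54.5%.
5. *60% applied only to retention, follow-up and adherence.* The 54 plays no part. No conflict.

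**Which reading the text supports**

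- The 60% rate in section 1.2 is tied to a span from the first trimester to six months after birth. That fits retention, follow-up and adherence. It cannot describe a three-month enrolment period (12.1).
- Section 11.1 counts recruitment against six per group, that is, against a target.
- The 50% for the community health centre is used in sections 6.3 and 11.0 as a share of the women recruited, not of those screened.
- The 54 answers a screen-failure question. It is a workload estimate and is never called a recruitment rate.
- Reading 1 makes the hypothesis unattainable on the plan's own forecast, which is a reason to doubt that it was meant.

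**The 11-to-18 overlap.** It arises only if 54 are in fact screened. The 54 is an expectation, not a fixed number: 18 enrolled from 30 or fewer screened meets readings 1 and 2 together.

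**Would a new threshold be better?** A bar of 18 of 54 would be met with probability 0.551 when the true yield is exactly one in three. A bar of 14 of 54 (26%) would be met with probability 0.905, but that figure has no basis in the documents. An on-forecast 18 of 54 would carry an exact (Clopper-Pearson) 95% interval of 21.1% to 47.5%. Neither bar is plainly better than leaving the measure descriptive.

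**The case for a change.** The strongest case for a change is that this is the endpoint, not a side issue. Section 2.1 rests the study on feasibility, section 6.3 says recruitment is under investigation, and section 5.2 ties the larger trial to the hypotheses. Being a pilot does not excuse an undefined criterion, and a few words in sections 1.2, 5.1 and 11.0 would settle it at no cost in participants or data. Enrolled/screened is also not far-fetched, since it is the only recruitment yield for which the plan supplies both numbers.

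Part of this stands. No definition is given anywhere, and the gap extends to retention, follow-up and adherence. Adherence, which could be a share of sessions, of minutes or of women, is arguably the more consequential omission in an exercise study. Stating the denominators would be tidier.

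The claim that following the plan leads to a wrong result does not stand. The 60% belongs to a working hypothesis assessed descriptively. There is no test and no formal stop/go rule, and section 5.2 says only that a larger study follows if the hypotheses are supported. Describing eligibility and recruitment means reporting how many women were screened, eligible and enrolled. From those three counts a reader can form every ratio above, so a denominator chosen late could not be concealed.

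**Conclusion.** No change is called for. The five measures in Aim 1 lack stated numerators and denominators, but this is missing detail that analysts can fill sensibly. The 33.3% against 60% comparison is correct arithmetic on a reading the plan does not state and its wording disfavours. Against the target of 18 the forecast is 100%; requiring 60% at both screening steps leaves a near miss (33.3% against 36%); and if the rate covers only what happens after enrolment there is nothing to compare.

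This rests on two assumptions: that the screened, eligible and enrolled counts are reported, as the descriptive analysis in section 5.1 implies, and that the 60% is used as a descriptive benchmark and not as a binding decision rule. If the sponsor made it a binding rule for starting the larger trial, the denominators would need to be fixed before the data are seen.

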## 7.0 Inclusion and Exclusion Criteria

7.1 *Describe, in bullet points, the criteria that define who will be included in this study:*

- Adult pregnant women (i.e. 18 years of age and older)
- Low risk, singleton pregnancy
- In first trimester of pregnancy (6 to 13 weeks gestation)
- Without absolute contraindications to moderate intensity exercise during pregnancy as defined by the American College of Obstetricians and Gynecologists
- Exercise clearance from OB/GYN

7.2 *Describe, in bullet points, the criteria that define who will be excluded from this study:*

- Pregnancies greater than low risk for any reason
- Pregnant with more than one fetus
- Absolute exercise contraindications and/or lack of exercise clearance from OB/GYN

7.3 *Indicate whether you are specifically recruiting or targeting any of the following special populations in your study using the checkboxes below.*

- Adults unable to consent (*complete and upload Supplemental Form A*)
- Minors (under 18 years old)
- Pregnant women
- Prisoners

6.4 *Indicate if you will include minorities (American Indians, Alaskan Native, Asian, Native Hawaiian, Pacific Islander, Black [not of Hispanic origin] and Hispanic) as Federal mandates require that you include minorities unless you can justify their exclusion*

- Yes
- No, Justify:

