## 10.0 Recruitment Methods

- N/A: Subjects will not be recruited.

10.1 Describe source of subjects: When, where, and how potential subjects will be recruited.

*NOTE: Recruitment refers to how you are identifying potential participants and introducing them to the study; for example, physician referral, database search, reviewing medical records, research participant groups/help/advocacy groups, advertising companies, call centers, in person announcements / presentations, etc.*

Participants will be recruited via physician referral, posted flyers and internet postings (e.g. local mom's groups, Upstate announcements, Department of Physical Therapy Education Facebook page, etc)

*10.2 Describe how you will protect the privacy interests of prospective subjects during the recruitment process.*

*NOTE: Privacy refers to an individual's right to control access to him or herself. This is NOT asking about confidentiality of data.*

All screening and information exchanges with prospective participants will happen in private (in a one on one setting).

*10.3 Identify all materials that will be used to recruit subjects and upload copies of these documents (such as telephone scripts, flyers, questionnaires, posters, letters, e-mails, pamphlets, advertisements).*

Flyers, e-mails

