## **11.0 Research Methods & Procedures**

Provide a detailed description of the methods and procedures that will be used to carry out the study. Include a summary of study visits and procedures (i.e., schedule of events table) in the space below or as an attachment.

Please make sure to include:

- Dosing of drugs and other details of study drug administration and study treatments
- A list and description of any experimental procedures
- A list and description all tests & procedures that would no be done if the subjects were not in the study
- An explanation how study participation differs from the standard of care
- Procedures being performed to monitor subjects for safety or to minimize risks

Eighteen low risk pregnant women with a singleton pregnancy will be recruited for this pilot project from Syracuse Community Health Center (50%), University OB/GYN Associates, and Upstate Community OB/GYN. All women will be enrolled during the 1st trimester (6 to 13-weeks' gestation) and without absolute contraindications to moderate intensity exercise during pregnancy as defined by American College of Sports Medicine (ACSM) and American College of Obstetricians and Gynecologists (ACOG). All participants will be cleared for exercise by their OB/GYN. The ACSM and ACOG guidelines include 150 min/wk of cardiovascular activity at a moderate intensity; 2-3 days/week of resistance training; and 2-3 days/wk of flexibility training. Clearance will come exclusively from the OB/GYN.

Women will be randomly assigned to either UA, EX or HOMEEX. Women randomized to EX will attend three exercise classes/week at the Institute for Human Performance (IHP) and given flexibility to attend classes between the hours of 7:30a-6p, Mon-Fri. Each session will consist of: 5-min flexibility warm-up and cool-down; 40 min of moderate intensity calculated as 40-59% Heart Rate Reserve (HRR) along with Rating of Perceived Exertion (RPE) between 13-14; and 20 minutes of resistance with an additional 30 minutes of unsupervised home aerobic activity per week. The women will be given their choice of aerobic equipment or walking either track/treadmill to achieve a total of 40 minutes of moderate intensity exercise.

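### The Syracuse Community Health Center's 50% share of the sample is a weak measure of whether lower-resource women can be recruited and kept; clinic-specific counts and rates should replace it

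*Combined protocol and SAP*

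**What the plan says.** - **Hypothesis (1.2, Aim 1).** The main feasibility criterion is a 60% rate for recruitment, eligibility, retention, follow-up and adherence. A further hypothesis, labelled secondary and exploratory, reads: "we will be able to successfully recruit and retain 50% of our pregnant women from the Syracuse Community Health Center (primarily women with lower resources").
- **Plan (6.3 and 11).** Section 6.3 intends to recruit "low risk pregnant women with a singleton pregnancy from Syracuse Community Health Center (50%), University OB/GYN Associates, and Upstate Community OB/GYN". Section 11 says the eighteen women "will be recruited for this pilot project from Syracuse Community Health Center (50%), University OB/GYN Associates, and Upstate Community OB/GYN".
- **Numbers (6.1, 6.2, 12.1).** Enrolment is "No more than 18 total participants (six per group"), to be completed in three months. The number to screen is "54 (anticipate that for every three women screened, one will participate in the study"). Neither figure is split by source.
- **Eligibility and channels (7, 9.1, 10.1).** The criteria cover age, a low-risk singleton pregnancy, gestation, contraindications and clearance; none names a clinic. Section 9.1 screens women who answer internet requests or flyers. Section 10.1 lists physician referral, flyers and "internet postings (e.g. local mom's groups, Upstate announcements, Department of Physical Therapy Education Facebook page, etc").
- **Analysis (5.1, repeated in 11).** Recruitment, eligibility, retention, follow-up and adherence are summarised descriptively. No breakdown by clinic is stated.

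No text says whether the 50% is a reserved quota or a target, or how a woman from a fourth practice is handled.

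**The concern.** Section 1.1 gives the lack of inner-city women in randomised trials of exercise in pregnancy as a reason for the pilot, and section 6.3 says the recruitment findings will shape the larger trial's recruitment plan. The question for SCHC is therefore how many women must be screened to enrol one, whether the places can be filled in the window, and how many women stay to 6 months after birth.

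A share of all enrolled women answers a different question: how SCHC did relative to the other sources. It can be met when recruitment has failed everywhere, and missed when SCHC recruited well but other sources recruited better. A larger trial planned from it could be given the wrong screening load for the population it most wants to reach.

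**Working it through.** **1. The plan's own figures.** 3 groups × 6 = 18. At three screened per participant, 18 × 3 = 54. Both reproduce. The planned SCHC number is 0.5 × 18 = 9.

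**2. Share and rate are different quantities.** Let *a* be the number approached and *r* the proportion of them who enrol, with subscripts S for SCHC and O for other sources. The SCHC rate is r_S. The share is a_S·r_S / (a_S·r_S + a_O·r_O), so it contains the other sources' numbers and rate.

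**3. One share, many rates.** Suppose 9 of 18 are from SCHC, a 50% share. The numbers approached below are an assumed range:

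| SCHC women approached | SCHC rate |
|---|---|
| 15 | 9/15 = 60% |
| 18 | 9/18 = 50% |
| 27 | 9/27 = 33% |
| 45 | 9/45 = 20% |
| 90 | 9/90 = 10% |

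**4. One rate, many shares.** With equal numbers approached, the share is r_S/(r_S + r_O). Hold r_S at 33% and vary r_O (assumed values):
- r_O = 10%: 0.333/0.433 = 77%
- r_O = 33%: 0.333/0.667 = 50%
- r_O = 60%: 0.333/0.933 = 36%

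The result labelled SCHC moves by 41 percentage points with no change at SCHC.

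**5. No minimum total.** Eighteen is a ceiling. If only 6 women enrol and 3 are from SCHC, 3/6 = 50% meets the share with a third of the planned SCHC number.

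**6. Quota or target.** If 9 places are reserved and all 18 fill, the share is 9/18 by design. If nothing is reserved, the share can vary. Treating each of 18 enrolled women as independently from SCHC with probability *p* (assumed), the binomial probability of at least 9 is 0.06, 0.26, 0.59 and 0.87 for *p* = 0.3, 0.4, 0.5 and 0.6.

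**7. Retention read as a share.** Start from 9 SCHC and 9 other women.
- 5 retained in each: 5/10 = 50%, so the share is met, although SCHC retention is 5/9 = 56%, below the 60% of the main hypothesis.
- 8 SCHC and all 9 others retained: 8/17 = 47%, so the share is missed, although SCHC retention is 8/9 = 89%.

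**8. What clinic-specific figures would give.** Exact (Clopper–Pearson) 95% limits for *x* of *n* are the 2.5% point of Beta(x, n−x+1) and the 97.5% point of Beta(x+1, n−x).
- Enrolled out of screened, if the 1-in-3 ratio holds at SCHC: 9 × 3 = 27 screened, 9/27 = 33% (17% to 54%).
- If 90 had to be screened (assumed): 9/90 = 10% (5% to 18%).
- Retention: 5/9 = 56% (21% to 86%); 6/9 = 67% (30% to 93%).
- For comparison, the share itself: 9/18 = 50% (26% to 74%).

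**The case against.** **A planned mix that is also the hypothesis is normal in a feasibility study.** This stands. A reader might infer that the hypothesis is circular, with success certain. The documents do not support that. No text makes the 50% an enforced quota; the total is only capped, within three months, so reserved places could go unfilled; and nothing in the enrolment plan fixes retention to 6 months after birth.

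**Without a quota the share can fail, so it carries some information.** Also true. A reader might go further and take the probabilities in step 6 as the plan's chance of missing its target. They are not: the values of *p* come from no document, and no text says that places go to whoever responds first.

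**Sections 6.3 and 11 name the sources, and section 10.1 only lists channels.** They can be read together, and physician referral is among the channels. That women from any practice will be admitted is therefore an inference from the silence of sections 7 and 9.1. The mismatch needs reconciling; it is not a settled rule.

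**The hypothesis is exploratory, and descriptive statistics could be split by clinic later.** The first part limits how much weight the point bears. The second depends on the clinic being recorded. Obstetric clearance before randomisation would probably identify the practice of women who enrol, but section 9.1 states no such record for women screened and not enrolled, and they belong in the missing denominator.

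**Section 1.2 might mean half of SCHC women, not half of the sample.** The wording allows it. But sections 6.3 and 11 use the 50% as a source mix, and 6.2 expects only 1 in 3 screened women to take part. If a rate was meant, its denominator still has to be stated.

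**Conclusion.** The point holds in limited form: the 50% share alone is a weak measure of recruitment and retention at SCHC. The algebra in step 2 needs no assumption. The sizes (a 10% to 60% SCHC rate behind one share; a 36% to 77% share behind one rate) rest on assumed numbers approached and assumed recruitment rates, and show how far the measure can mislead rather than what will happen. The 9-of-27 figure assumes that the plan's overall screening ratio applies at SCHC.

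The documents do not show that the pilot can learn nothing about lower-resource women. The count of SCHC women enrolled and their retention would be informative if reported against their own denominators. The change is worth making because it concerns a stated purpose of the pilot, costs little, and is hard to make once screening has run without a clinic record.

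**What to change.** 1. **Screening log (9.1).** Record the prenatal clinic of every woman screened, including those who do not enrol.
2. **Hypothesis (1.2) and analysis (5.1, 11).** Replace the 50% share with three SCHC results, each beside the non-SCHC figure. Give the proportions with exact 95% intervals:
   - whether 9 SCHC women were enrolled within the three-month window;
   - SCHC women enrolled out of SCHC women screened (9 of 27 if the plan's ratio holds there);
   - SCHC women retained to 6 months after birth out of SCHC women enrolled.
3. **Status of the 50% (6.3, 11).** Say whether it is a reserved quota or a target. If it is a quota, say how places are held and what happens if they are unfilled at three months.
4. **Source population.** Reconcile the three clinics in 6.3 and 11 with the open criteria and advertising in 7, 9 and 10. Either direction works: limit eligibility to the three clinics, or widen 6.3 and 11. Limiting narrows the pool in a short window; widening needs a rule for counting women from other practices.

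**Cost.** One log field and some wording. With about 9 SCHC women the intervals will be wide, so the results should be presented as planning estimates. If places are reserved, enrolment may run slower, and that delay should be reported as a feasibility finding.

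### Aim 2 asks each measure to detect change in both six-woman exercise arms; read as a 5% test in each arm, a moderate real change often fails, so responsiveness should be estimated rather than tested arm by arm

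*Combined protocol and SAP*

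**What the plan says.** All references are to the combined protocol and SAP.

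- **Section 1.2, Specific Aim #2:** "Our working hypothesis is that the above outcome measures will be able to detect changes in maternal outcome measures in both exercise groups".
- **Section 2.1:** the endpoint is whether the study is feasible and "if the planned outcome measures are appropriate for detecting change in the maternal dependent variables in all three participant groups". This is three groups, where Aim 2 names two.
- **Section 5.1, repeated in section 11.0:** "Kruskal-Wallis and Friedman's ANOVA will be used to investigate between group and within group differences". Friedman's test is the only method named for change over time. No alpha, responsiveness threshold, multiplicity rule or missing-data rule is given.
- **Section 5.2:** "If the working hypotheses are supported, the next phase will be a large, randomized intervention study". It also says: "Pilot data from this project can be utilized in the power analysis for the larger study". No power calculation is offered.
- **Section 6.1:** at most 18 women, six in each group.
- **Section 11.0:** questionnaires are given at baseline, 25-26 weeks, 37-38 weeks and monthly to six months after birth (nine occasions). The treadmill test is done at baseline and at three and six months after birth (three occasions).
- **Section 1.2, Aim 1:** the working rate is "retention, follow-up and exercise adherence from 1st trimester through 6-months post-natal at a 60% rate".

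**The concern.** Aim 2 asks whether an instrument can register change. As worded, that is tied to detection in each exercise arm separately, and the only tool supplied is a rank test on six women or fewer. If a measure must pass in two arms, the chance of support is the product of two small chances. An instrument that responds well to a moderate change could then fail to show detection in both arms simply because each arm is small. Since section 5.2 makes the next phase follow from supported hypotheses, a null result of that kind would count against the measure, and to some degree against the larger trial, without saying much about either. The difference between two groups (1.2) and three (2.1) leaves it unclear which comparison is even meant.

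**Working it through.** **Inputs from the documents.** Six women per arm; 12 in the two exercise arms (EX and HOMEEX); 18 in all. Nine questionnaire occasions; three treadmill occasions. Retention 60%: 6 × 0.6 = 3.6 (about 4), 12 × 0.6 = 7.2 (about 7), 18 × 0.6 = 10.8 (about 11).

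**Assumptions, because the plan gives none.** Test level 5%; normal scores; equal correlation between a woman's occasions; the same true change in each arm unless stated. The plan has no power figure of its own to reproduce.

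**Method.** Friedman power was simulated, with critical values simulated under no change. The arms contain different women, so P(both arms) = (power in one arm)². The rise-and-fall profile is the peak change times 0, 0.5, 1, 0.6, 0.45, 0.3, 0.2, 0.1, 0 over the nine occasions.

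| True change | Correlation | One arm (6) | Both arms | 12 pooled | 18 pooled |
|---|---|---|---|---|---|
| Rise and fall, peak 0.5 SD | 0.6 | 15% | 0.15² = 2% | 30% | 46% |
| Rise and fall, peak 0.7 SD | 0.6 | 27% | 0.27² = 7% | 57% | 80% |
| Rise and fall, peak 1.0 SD | 0.6 | 54% | 0.54² = 29% | 91% | 99% |
| Treadmill, 3 occasions, linear 1.0 SD | 0.6 | 35% | 0.35² = 12% | 75% | 93% |

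If section 2.1 is read as detection in each of three groups, and the control group changes alike, the 0.7 SD case becomes 0.27³ = 2%.

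**Sensitivity to the pattern.** A sustained step after birth of 0.7 SD over nine occasions passes both arms 39% of the time at correlation 0.6, 60% at 0.7 and 87% at 0.8. A 1.0 SD step at correlation 0.6 passes 88% of the time. The rise-and-fall profile with peak 1.0 SD at correlation 0.8 passes about 76%.

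**Retention, applied to both sides** (rise and fall, peak 0.7 SD, correlation 0.6). Friedman's test needs complete rows.
- Four women per arm: 17% in one arm, 0.17² = 3% in both.
- Seven of 12 pooled: about 33%, not 57%.
- Eleven of 18 pooled: about 53%, not 80%.

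**What pooling gives up.**
- *Change in one exercise arm only* (rise and fall, peak 1.0 SD, correlation 0.6): 12 pooled detect it about 22% of the time, against 54% for that arm tested alone.
- *No change in either arm:* the both-arms rule passes 0.05² = 0.25% of the time and a pooled 5% test 5%, which is 20 times as often.

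**The case against.** The strongest reply is that the plan contains no such decision rule. Section 5.1 says only that the tests "will be used to investigate between group and within group differences". It sets no alpha and no verdict per instrument, and section 5.2 also intends the data for planning the larger study. This stands. A reader might infer that good instruments will usually be declared inappropriate and the next trial blocked. The documents do not say that an instrument failing a test is rejected, and *usually* does not survive the sensitivity analysis: with a sustained step, a high correlation or a larger change, both arms often pass.

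A reader might also infer that pooling cures the problem at no cost, or that the 18 women could settle Aim 2. Neither is supported. Pooling changes the question from both groups to the average woman, dilutes a change confined to one arm, and passes more often when nothing changes. The pilot sets out to study two delivery modes, so unlike responses are plausible. Pooling all 18 adds controls, and movement over pregnancy and recovery is not evidence of an exercise effect. At the plan's own 60% retention, the pooled figures fall well short of those for full enrolment.

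What the reply does not remove is that the hypothesis is phrased as detection, is to be supported or not, and comes with significance tests as its only stated means. Leaving the criterion unwritten invites the per-arm reading.

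**Conclusion.** The point holds in a limited form. Aim 2 has no operational criterion, its groups differ between 1.2 and 2.1, and the most natural reading of the text (Friedman's test in each exercise arm) is weak for moderate change. Under an assumed 5% level and correlation 0.6, a 0.7 SD rise-and-fall change is found in both arms about 7% of the time, and a linear 1.0 SD change on the treadmill test about 12%. These are conditional figures: for a sustained 0.7 SD step the both-arms rate runs from 39% to 87% over correlations 0.6 to 0.8. The conclusion is that per-arm significance in six women is a poor yardstick for responsiveness. It is not that the plan commits itself to rejecting sound measures.

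**What to change.** 1. In 1.2, 2.1 and 5.1 (and the copy of the analysis text in 11.0), name one set of groups for Aim 2.
2. State that responsiveness is judged by estimation and that support for Aim 2 does not require significance in each arm.
3. For each instrument, report the standardised response mean with 95% CI from baseline to named later occasions at which that instrument is measured: for questionnaires, for example, 25-26 weeks, 37-38 weeks and six months after birth; for the treadmill test, three and six months after birth. Add completion counts and, for the questionnaires, floor and ceiling counts.
4. Give these per arm, plus an arm-stratified pooled estimate for EX and HOMEEX, with all women as a further supplement.
5. State how incomplete rows are handled. Section 18.3 keeps data up to withdrawal, but Friedman's test cannot use a partial row.
6. Label the pooled result: it shows that the measure moved, not that exercise moved it, and it can hide a change confined to one arm.

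The cost is a few sentences and no extra data. The estimates will be imprecise. In units of the SD of change, the 95% half-width for a mean change is about 2.571/√6 = 1.05 in one arm and, with the SD pooled within arms, 2.228/√12 = 0.64 for the two exercise arms at full retention. A 0.7 SD change at correlation 0.6 is 0.7/√(2 × 0.4) = 0.78 on that scale. The intervals would show this uncertainty openly, which a failed test in one arm does not.
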